## 9.4 Halting Rules

If in the opinion of the Investigator, the participation in the study is or is becoming detrimental to the well-being of a particular subject, this issue should be discussed with the Medical Monitor for this study and a determination made regarding dose reduction, interruption, or withdrawal of the subject from the study.

Withdrawal of the subject from the study should be considered if:

- ALT or AST  $> 8 \times$  ULN
- ALT or AST  $> 5 \times$  ULN for more than 2 weeks
- ALT or AST  $> 3 \times$  ULN and (total bilirubin  $> 2 \times$  ULN or INR  $> 1.5$ )
- ALT or AST  $> 3 \times$  ULN with the appearance of fatigue, nausea, vomiting, right upper quadrant pain or tenderness, fever, rash, and/or eosinophilia ( $> 5\%$ )

For subjects with known liver metastasis and elevated ALT or AST of  $\leq 5 \times$  ULN at baseline, discontinuation of treatment should be considered if:

- ALT or AST  $> 5 \times$  ULN and total bilirubin  $> 2 \times$  ULN

All subjects discontinued from the study should be followed until abnormal values return to normal.

ALL DISCONTINUATIONS SHOULD BE DISCUSSED WITH THE MEDICAL MONITOR PRIOR TO DISCONTINUATION.

If any 2 out of the first 10 subjects enrolled in the study meet the above hepatotoxicity criteria, or if a total of 5 subjects ever meet these criteria and hepatotoxicity is not attributable to an underlying condition (i.e. liver progression), then the 18 mg dose will be reduced to 9 mg for all subjects; i.e., all subjects that are receiving 18 mg will be reduced to 9 mg and all newly enrolled subjects will receive a 9 mg dose. If any of these criteria are met in a total of 5 subjects following the study wide reduction to the 9 mg dose, the study will be halted (i.e., there will be no dose reduction, only study drug discontinuation).

## 9.5 Safety Oversight

In order to protect the safety of the subjects, an SMC will be established for the study to review the safety data on an ongoing basis. The SMC will consist of, as a minimum, the Medical Monitor, a Safety Reviewer with an oncology background, a statistician, and two GTx, Inc. representatives, consistent with the SMC charter.

Protocol: A Phase 2 Open Label, Multi-Center, Multinational Study Investigating The Efficacy and Safety Of GTx-024 On Advanced, Androgen Receptor-Positive Triple Negative Breast Cancer (AR+ TNBC)	Compound No.: GTx-024 Author: [name]
---	---

The Medical Monitor will be a physician with relevant expertise whose primary responsibility is to provide independent safety monitoring in a timely fashion through review of AEs, immediately after they occur or are reported, with follow-up through to resolution. The Medical Monitor will evaluate individual and cumulative participant data when making recommendations regarding the safe continuation of the study.

The Medical Monitor will be selected based on relevant study-related or therapeutic expertise and participation is for the duration of the study. The Medical Monitor will be able to readily access participant records in real time.

Protocol: A Phase 2 Open Label, Multi-Center, Multinational Study Investigating The Efficacy and Safety Of GTx-024 On Advanced, Androgen Receptor-Positive Triple Negative Breast Cancer (AR+ TNBC)	Compound No.: GTx-024 Author: [name]
---	---

## 10 CLINICAL MONITORING

The purpose of the site monitoring visit is to ensure that the study is being conducted in accordance with the protocol (and any subsequent amendments), current ICH Guidelines on Good Clinical Practice (GCP) requirements, and applicable IRB/IEC and regulatory requirements.

An authorized study monitor (clinical research associate [CRA]) will visit the site prior to initiation and at periodic intervals to review the study records (including ICFs, inventory of study drug, and eCRFs), and assess compliance with the study protocol. The monitor(s) will also visit at conclusion of the study to help resolve any remaining data queries and close out all record keeping.

It is the responsibility of the Investigator to make sure all necessary source documentation and records are available to the CRA during his/her visit and to provide a suitable space for the CRA to review these documents. Additionally, the Investigator must also be available as needed during the monitoring visit. It is the CRA's responsibility to arrange the visits with the unit in advance and to notify the unit of the documentation that he/she will need during the visit.

All findings resulting from monitoring visits will be documented and shared with the Investigator and Sponsor via follow-up letters and monitoring reports. As much as possible, issues/discrepancies should be resolved during the monitoring visits, but those remaining at the end of the visit will be followed through until resolution.

Protocol: A Phase 2 Open Label, Multi-Center, Multinational Study Investigating The Efficacy and Safety Of GTx-024 On Advanced, Androgen Receptor-Positive Triple Negative Breast Cancer (AR+ TNBC)

Compound No.: GTx-024  
Author: [name]

## 11 STATISTICAL CONSIDERATIONS

This section is an overview of the statistical design and its rationale. A separate Statistical Analysis Plan (SAP) will provide further details of statistical tests, handling of missing data, and various methods for imputing time-to-event to account for the difference between the last known event free time and the subsequent first event date, as well as specifications of tables, figures, and listings.

### 11.1 Study Hypotheses

This trial will employ a Simon's two-stage (optimal) design. The assumptions for the design are as follows:

- $H_0$ : CBR  $\leq$  0.05
- $H_1$ : CBR  $\geq$  0.20
- $\alpha$  = 0.05 (one sided)
- Power = 90%

### 11.2 Sample Size Considerations

Based on the above assumptions, a sample size of N = 41 TNBC subjects with centrally confirmed AR+ status who received at least one dose of study treatment (evaluable subjects) are needed if the trial continues to completion of the second stage. The trial will proceed to the second stage if at least 2 subjects among the first 21 evaluable subjects achieve CB, defined as SD, PR, or CR as per RECIST 1.1. If the trial proceeds to the second stage, a statistical success that favors further evaluation of GTx-024 18 mg in future trials will require at least 5/41 subjects to achieve CB at week 16, i.e., the null hypothesis of an unacceptably low rate of CB,  $\leq$  5.0%, can be rejected in favor of the alternative hypothesis that indicates the higher rate, 20%, is more likely. The lower limit of the exact 90% confidence interval at exactly five CBs, 6.1%, exceeds 5.0%. At any time during the first stage, if two subjects achieve CB at week 16, the trial will proceed to the second stage; otherwise, it will be halted for lack of efficacy. If at any time, 5 subjects achieve CB at week 16, the efficacy criteria has been met; however, the trial should proceed to full accrual of 41 evaluable subjects in order to better characterize the CB rate, evaluate secondary endpoints, and describe the safety profile of the drug.

Subjects whose AR+ status is not centrally confirmed will be replaced in order to accrue the necessary number of evaluable AR+ subjects to be included in the primary analysis. Subjects who are not confirmed AR+ may remain on the trial, but will not be part of the primary efficacy analysis – these subjects will contribute to secondary and tertiary analyses as noted below. This may result in up to 14 additional subjects enrolled (a total of 55 subjects) to account for discordant local/central AR status results and for the rare subject who is enrolled but never received study drug.

Protocol: A Phase 2 Open Label, Multi-Center, Multinational Study Investigating The Efficacy and Safety Of GTx-024 On Advanced, Androgen Receptor-Positive Triple Negative Breast Cancer (AR+ TNBC)	Compound No.: GTx-024 Author: [name]
---	---

### 11.3 Planned Interim Analyses (if applicable)

The number of clinical benefit responses during Stage I of this Simon's Two-Stage design will determine whether the trial moves forward to Stage II. No interim analyses beyond this determination will be performed, thus no database lock will be necessary.

### 11.4 Final Analysis Plan

#### 11.4.1 Analysis sets

Full Analysis Set (FAS): All subjects who are enrolled and receive at least one dose of study drug.

Evaluable subjects: Subjects in the FAS who have centrally confirmed AR+ status; these subjects are the subjects in the primary efficacy analysis.

Per Protocol Set (PPS): All subjects with centrally confirmed AR+ who have baseline scans and complete the week 16 RECIST 1.1 evaluation, receive at least 80% of the anticipated 18 mg dose, and have no major protocol deviations.

Safety Analysis Set (SAS): All subjects who are enrolled and receive at least one dose of study drug.

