### 7.3 Treatment Phase

The first dose of study drug will be administered at baseline (Visit 2). GTx-024 will be administered for up to 12 months from the first dose of treatment or until disease progression (whichever is sooner), subject's withdrawal of consent, or intolerability. Subjects who benefit from the treatment at week 16 and still benefit from the treatment at week 24 may continue to receive GTx-024 for a total of 12 months from the date of the first dose of study treatment (as long as they still benefit from the treatment during these 12 months). Subjects who continue to demonstrate a beneficial response at 12 months will be offered to continue in a safety extension study under a separate protocol.

After randomization on Day 1, a safety check involving a comprehensive metabolic panel (Chem 14), including serum calcium and liver function tests, will be performed at Week 2 ( $\pm 3$  days). The Week 2 safety check should include a clinic visit. The investigator may repeat these checks at Week 3 ( $\pm 3$  days) if clinically indicated.

During the first 4 months of the treatment phase, the subjects will be asked to come for a visit every 4 weeks (Visits 3, 4, 5, and 6), and then every 8 weeks (Visit 8 and Visits 10–12 as required if still on treatment). Visits 7 and 9 at weeks 20 and 28 will only take place in subjects who have CR or PR at Visit 6 (week 16) or Visit 8 (week 24), respectively (see below).

The following tests and procedures will be performed during Visits 3, 4, 5, 6, and 8 in the treatment phase:

- Review concomitant medications
- Physical examination, including weight and vital signs (heart rate, respiratory rate, body temperature, blood pressure in a sitting position)
- ECOG performance status
- Blood sampling for: hematology, biochemistry, serum lipid profile, coagulation status, serum hormones, and PSA
- Urine analysis, only if clinically indicated
- Urine pregnancy test for premenopausal subjects (at the site)
- AE collection
- Subjects will be asked to complete a QoL questionnaire
- GTx-024 drug accountability/dispensation

Radiologic assessments for anti-tumor effect will be done every 8 weeks whilst subjects receive treatment (Visit 4, Visit 6, Visit 8, and thereafter). In addition, if a subject has CR or PR at Visit 6 (week 16) or Visit 8 (Week 24), in compliance with RECIST 1.1 guidelines, a confirmation of the CR or PR should be done 4 weeks later (i.e., Visit 7 and/or Visit 9, as

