#### 11.4.2 Definition of analysis endpoints; primary, secondary, tertiary, exploratory, and safety

##### Primary efficacy endpoint

Tumor response in terms of clinical benefit will be assessed by RECIST 1.1 criteria from centrally read CT scans obtained at the 16 week assessment. Tumor response is judged relative to baseline tumor assessments. An evaluable subject will be considered to have a response of CB if the assessment indicates SD, PR, or CR. The primary assessment is among the evaluable subjects in the FAS at 16 weeks. An evaluable subject who does not have a week 16 assessment for any reason remains in the evaluable subset of the FAS and is considered a failure to achieve CB (SD, PR, or CR).

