##### Secondary efficacy endpoints

- CBR in the FAS at 16 weeks.

The following secondary efficacy endpoints will be assessed among evaluable subjects (if not already listed above), the FAS (if not already listed above), and the PPS:

Protocol: A Phase 2 Open Label, Multi-Center, Multinational Study Investigating The Efficacy and Safety Of GTx-024 On Advanced, Androgen Receptor-Positive Triple Negative Breast Cancer (AR+ TNBC)	Compound No.: GTx-024 Author: [name]
---	---

- CBR at weeks 16 and 24
- ORR (PR or CR assessed by RECIST 1.1 criteria) at weeks 16 and 24.
- Best (confirmed) overall response rate (BOR). BOR is defined as the best observed response for each subject up to and including the EOT. Responses of PR or CR should be confirmed by a repeat assessment at least 4 weeks later.
- PFS: PFS is defined as the time from treatment initiation until objective tumor progression or death. Subjects who have no PFS events will be censored at the date of the last adequate tumor assessment. If the subject has no post-baseline tumor assessments, they will be censored at the time of enrollment.
- TTP: TTP is defined as the time from treatment initiation until objective tumor progression or death due to PD. Subjects who have not progressed will be censored at the date of the last adequate tumor assessment. If the subject has no post-baseline tumor assessments but was known to be alive, they will be censored at the time of enrollment.
- Duration of response: Duration of response, in responders, is defined as the period from the date of initial PR or CR until the date of PD or death from any cause. Only subjects with BOR of CR or PR (i.e., responders) will be included in the analysis of duration of response. Subjects with no documented progression or death after CR or PR will be censored at the last date at which they are known to have had the CR or PR.
- Overall Survival: OS is defined as the time from treatment initiation until death or date of last follow up to a maximum of 24 months post treatment initiation. Subjects known to be alive at their last follow up will be censored at that time.

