#### 11.4.3.2 Primary efficacy analysis

The primary efficacy analysis is based on rules as set forth in Simon's two-stage (optimal) design as previously described, and is based on the proportion of evaluable subjects in the FAS who achieve CB at 16 weeks. At least 2/21 subjects must achieve CB in order for the trial to proceed to the second stage. If the trial proceeds to the second stage,  $\geq 5/41$  subjects must have CB at 16 weeks to deem the efficacy criteria to have been met. This is the minimum number of successes needed to rule out an unacceptably low, 5%, CB rate (lower limit of the 90% confidence interval). The exact 90% and 95% confidence intervals about the CBR at week 16 will be constructed.

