#### 11.4.3.3 Secondary efficacy analysis

- The exact 90% and 95% confidence intervals about the CBR at week 16 among subjects in the FAS will be constructed.

The following secondary efficacy analyses will be performed, if not already done so above, among the evaluable subjects, the FAS, and the PPS:

- The exact 90% and 95% confidence intervals about the CBR at 16 and 24 weeks will be constructed.
- The exact 95% confidence interval about the ORR (PR or CR) will be constructed at weeks 16 and 24.
- The exact 95% confidence interval about the BOR will be constructed at weeks 16 and 24.
- PFS: Median PFS and 95% confidence intervals will be estimated by the Kaplan-Meier method and the survival function and associated 95% confidence intervals will be constructed at key time points.
- TTP: Median TTP and 95% confidence intervals will be estimated by the Kaplan-Meier method and the survival function and associated 95% confidence intervals will be constructed at key time points.
- Duration of response: Median duration of response and 95% confidence intervals will be estimated by the Kaplan-Meier method and the survival function and associated 95% confidence intervals will be constructed at key time points for responders.

Protocol: A Phase 2 Open Label, Multi-Center, Multinational Study Investigating The Efficacy and Safety Of GTx-024 On Advanced, Androgen Receptor-Positive Triple Negative Breast Cancer (AR+ TNBC)	Compound No.: GTx-024 Author: [name]
---	---

- Overall Survival: Median OS and 95% confidence intervals will be estimated by the Kaplan-Meier method and the survival function and associated 95% confidence intervals will be constructed at key time points. Follow up will be up to 24 months post treatment initiation for each subject and subjects alive at that time will be censored.

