#### 11.4.3.7 Missing data/Outliers/Dropout considerations

No imputation for missing data will be carried out other than to complete partial dates using standard imputation techniques as per the Contract Research Organization's (CRO's) standard.

No evaluable subject will have missing data for the primary efficacy analysis because subjects who have the week 16 assessment will be classified as having CB or not, and those who do not have a week 16 assessment will be classified as not having CB.

With regards to missing start and stop dates for AEs and medications, imputation rules will be provided in the SAP. In addition, rules to determine in which period each AE belongs for the summary tables will also be provided in the SAP.

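### The Per Protocol Set requires a completed week-16 evaluation with no exception for earlier progression or death, so it drops failures from week-16 CBR and makes OS conditional on surviving to about Day 105

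*Combined protocol and SAP*

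**What the plan says.** Section 11.4.1 admits to the PPS only centrally confirmed AR-positive subjects "who have baseline scans and complete the week 16 RECIST 1.1 evaluation, receive at least 80% of the anticipated 18 mg dose", and who have no major protocol deviation. Nothing there or elsewhere in the supplied text excepts a subject who progressed or died first.

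For the primary endpoint, Section 11.4.2 says that an evaluable subject without a week-16 assessment "remains in the evaluable subset of the FAS and is considered a failure to achieve CB". Section 11.4.3.7 repeats that "those who do not have a week 16 assessment will be classified as not having CB".

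Section 11.4.3.3 uses the PPS widely: "The following secondary efficacy analyses will be performed, if not already done so above, among the evaluable subjects, the FAS, and the PPS". The list that follows covers week-16 and week-24 CBR and ORR, BOR, PFS, TTP, duration of response and OS. The CBR gets exact 90% and 95% intervals. Section 11.4.2 fixes the OS clock: "OS is defined as the time from treatment initiation until death or date of last follow up".

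Section 7.3 continues treatment only until progression (12 months at most) and schedules scans every 8 weeks while treatment lasts. Appendix A puts the week-16 visit at Day 112 ± 7 days.

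**The concern.** Membership of the PPS depends on something that happens about 15 weeks after the time origin, and the outcome itself helps decide it. A subject who progresses at the week-8 scan stops treatment and normally has no week-16 scan, so she leaves the set. A subject who dies before the window opens always leaves. A subject whose progression is first seen at week 16 stays.

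For week-16 CBR and ORR, this criterion therefore takes out non-responders and no responders. For OS, it guarantees survival to about Day 105 while the result is still described as survival from first dose. PFS and TTP are selected in the same direction, though not absolutely. Treatment follows the local read and efficacy the central read (Section 8.1), so a subject with central progression at week 8 can still reach week 16.

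No trial decision is at stake. The risk is interpretive: a PPS result better than the evaluable-set result could be credited to good compliance when it comes from discarding early progressions and deaths.

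**Working it through.** **Inputs from the protocol.** 41 evaluable subjects and success at 5/41 (11.2); lower 90% limit of 6.1% at 5/41 (11.2), compared with 5% (11.4.3.2); a missing week-16 assessment counts as failure (11.4.2, 11.4.3.7); week-16 window opens on Day 112 − 7 = Day 105, or 15 weeks (Appendix A).

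**Assumed, because the documents do not give them.** m, the number of the 41 without a week-16 evaluation, from 4 to 20. Its split into m1 (progression or death first) and m2 (other withdrawals, such as intolerance, Section 5.4.3), with m1 from half to all of m. Median OS of 6 to 15 months and the hazard shape.

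**The plan's own figures.** The rule 2/21 then 5/41 has type I error 0.0457 at a CBR of 5% and power 0.9017 at 20%, as planned. For the interval I took, at each p, the shortest run of counts with at least 90% probability, and then the smallest p whose run contains the observed count. This is the family of methods that Section 11.2 cites. It gives 6.1% at 5/41, matching the plan. Clopper-Pearson gives 4.93%, so it is not the plan's method and is not used below.

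**Week-16 CBR.** Every subject removed by this criterion is a failure, so x benefits read x/(41 − m) in place of x/41. With the fix they read x/(41 − m2). For x = 5 (5/41 = 12.2%):

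| m | PPS as written | Factor 41/(41 − m) | PPS after fix, m2 = 0 to m/2 | Points removed by fix |
|---|---|---|---|---|
| 4 | 5/37 = 13.5% | 1.11 | 5/41 to 5/39 = 12.2–12.8% | 1.3–0.7 |
| 10 | 5/31 = 16.1% | 1.32 | 5/41 to 5/36 = 12.2–13.9% | 3.9–2.2 |
| 20 | 5/21 = 23.8% | 1.95 | 5/41 to 5/31 = 12.2–16.1% | 11.6–7.7 |

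Week-16 ORR scales by the same factor, because Section 3.2.2 defines objective response as attained at that assessment.

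**Against the 5% reference.** With the same interval method, 4/41 misses the success rule and has a lower limit of 4.3%. If 6 of its 37 failures are dropped, the PPS shows 4/35 with a lower limit of 5.1%. Restoring one of the six gives 4/36 and 4.9%.

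**OS.** With Weibull survival S(t) = exp(−(t/λ)^k), the median among those alive at 15 weeks is t* = λ[(15/λ)^k + ln 2]^(1/k). The shift is t* minus the unconditional median. Worked case: k = 2, median 9 months = 39.1 weeks, λ = 39.1/√(ln 2) = 47.0, t* = 47.0 × √(0.102 + 0.693) = 41.9, shift 2.8 weeks.

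| Shape k | Shift in weeks for medians of 6 / 9 / 12 / 15 months |
|---|---|
| 0.8 | 22.4 / 23.9 / 25.1 / 26.1 |
| 1.0 (constant hazard) | 15.0 / 15.0 / 15.0 / 15.0 |
| 1.5 | 7.1 / 6.0 / 5.2 / 4.7 |
| 2.0 | 4.0 / 2.8 / 2.1 / 1.7 |

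Under a constant hazard, 33%, 23%, 18% and 15% of subjects would die before Day 105 at these medians and could not enter the PPS. Any further OS selection from losing early progressors is not counted.

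**The case against.** The strongest reply is that little hangs on the PPS. The primary CBR and both Simon rules use the evaluable set with missing counted as failure, and there is no PPS success rule. Evaluable and FAS results are reported alongside, so a shrunken denominator is visible. Sections 3.1 and 3.2.2 list the secondary objectives and measures for the evaluable subset and the FAS only; the PPS enters in Section 11. All of this stands and limits the weight of the point.

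A completer set is also a recognised choice, and the definition is open about what it requires. That is fair for withdrawals unrelated to outcome. It does not cover exclusion caused by progression or death.

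The sizes rest on assumptions, and the 4/41 example was chosen at the threshold. That is true. The entry rules (life expectancy under 4 months excluded; ECOG 0 or 1) should make early deaths less common, which points to the smaller OS shifts. The dose and deviation criteria can remove successes too, so the net shift in the realised PPS is not fixed. Only the direction of the week-16 criterion taken alone is certain.

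Some early progressors may still be scanned. Section 5.4.4 promises efforts to continue evaluations after withdrawal, and an end-of-treatment scan (Sections 7.4 and 7.6) might fall in the week-16 window, though Section 11.4.1 does not say whether it would count. This could reduce the loss but cannot help those who have died. Finally, Section 11 defers details to a separate SAP. It may refine the definition, but nothing in the supplied text does.

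**Conclusion.** The concern holds and should be fixed. Followed exactly, Section 11.4.1 gives a PPS whose week-16 criterion removes only CBR failures and whose OS is conditional on survival to about Day 105. The direction follows from the plan's own missing-equals-failure rule and visit window; the size does not. For m of 4 to 20, five benefits read 13.5% to 23.8% in place of 12.2%. The part the fix can repair is 0.7 to 1.3 points at m = 4 and 7.7 to 11.6 points at m = 20, if early progression or death accounts for half to all of m. The median OS shift is 1.7 to 26 weeks over the shapes and medians tried. The primary result is untouched, and there is no contradiction with Section 11.4.2, whose failure rule is written for the evaluable set.

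**What to change.** Add one paragraph to Section 11.4.1 and the SAP:

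1. The evaluation criterion is met by either a completed week-16 evaluation or death or documented progression before week 16.
2. Progression is by central read, as for the efficacy endpoints. A subject stopped for local progression, without central confirmation and without a week-16 scan, is kept and counted as a CBR failure; her PFS and TTP follow their Section 11.4.2 definitions.
3. Subjects admitted by the second route are failures for CBR and ORR. They are PFS, TTP or OS events only where the definition makes them so.
4. For these subjects only, the 80% dose criterion is computed over the time to progression or death. Section 11.4.1 states no denominator, and without this step the dose criterion could remove them again.
5. Subjects who leave before week 16 for any other reason stay outside the PPS and are reported by number and reason.

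If the present set is kept for any analysis, label its CBR as among week-16 completers, and its PFS, TTP and OS as conditional on reaching week 16.

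The cost is the paragraph itself. No new data or visits are needed and the Simon rules do not change. PPS figures become less favourable, and the set will include some subjects with short exposure.
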